8.2. Subject Exclusion Criteria

1. The presence of any of the following will exclude a subject from study enrollment: Any chronic liver disease other than NASH (i.e., drug-induced, viral hepatitis, autoimmune hepatitis, primary biliary cirrhosis, primary sclerosing cholangitis, hemochromatosis, A1AT deficiency, Wilsons disease)
2. Cirrhosis, as assessed clinically or histologically
3. Presence of vascular liver disease
4. BMI \leq 25 kg/m²
5. Excessive alcohol use ($>$ 20 g/day) within the past 2 years

6. AST or ALT > 250 U/L.
7. Type 1 diabetes mellitus
8. Bariatric surgery in the past 5 years.
9. Weight gain or weight loss of > 5% in past 6 months or > 10% change in past 12 months.
10. Contraindication to MRI
11. Inadequate venous access
12. HIV antibody positive, hepatitis B surface antigen positive (HBsAg), or HCV RNA positive.
13. Receiving an elemental diet or parenteral nutrition
14. Chronic pancreatitis or pancreatic insufficiency
15. Any history of complications of cirrhosis (i.e. ascites, hepatic encephalopathy, or portal hypertensive bleeding), even if absent or optimized with medical management at time of screening
16. Concurrent conditions:
 - a) Inflammatory bowel disease
 - b) Unstable angina, myocardial infarction, transient ischemic events, or stroke within 24 weeks of screening
 - c) Ongoing infectious, immune mediated disease within previously 1 years
 - d) Any malignant disease (other than basal cell carcinoma of the skin) within previous 2 years
 - e) Prior solid organ transplant
 - f) Any other concurrent condition which, in the opinion of the investigator, could impact adversely on the subject participating or the interpretation of the study data.
17. Concurrent medications including:
 - a) Anti-NASH therapy(s) initiated after the liver biopsy diagnosing NASH. Anti-NASH therapies include S-adenosyl methionine (SAMe), milk thistle, and vitamin E.
 - b) Antidiabetic mediation which may impact NASH histology initiated after the liver biopsy diagnosing NASH including thiazolidinediones (glitazones), dipeptidyl peptidase 4 inhibitors (gliptins) or glucagon-like peptide 1 analogs.
 - c) Immune modulatory agents including systemic steroids, methotrexate, anti-TNF- α therapies (infliximab, adalimumab, etanercept) or anti-integrin therapy (namixilab).
 - d) UGT2B7 enzyme inhibitors (e.g., diclofenac, fluconazole, medroxyprogesterone acetate, meclofenamic acid)

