10.3.2 Screening Period (within 4 weeks before randomization)

Prior to performing any study procedures, an informed consent form will be reviewed and signed by each subject. Subjects will be screened within 4 weeks before starting study treatment to determine eligibility for participation in the study, unless otherwise noted below. Subjects who fail to meet eligibility due to an abnormal laboratory results (other than what is otherwise explained by NAFLD alone) may undergo retesting of the abnormal laboratory test during the screening window. This will be done at the discretion of the investigator and with prior approval from the Sponsor or Medical Monitor.

Sufficient time should be allowed for all screening laboratory studies to be resulted prior to scheduling subject for MRI testing. The following will be performed and documented at screening:

- Obtain subject screening number
- Obtain medical history and complete physical examination
- Record vital signs (blood pressure, heart rate, respiratory rate, body temperature)
- Record height, weight and body mass index
- Study pathologist to review screening liver biopsy (within 12 months of screening) for confirmation and staging of NASH as defined by NASH Clinical Research Network (NASH CRN) Grading and Staging System [28].
- MRI to be performed and study radiologist to review and confirm > 6% hepatic steatosis for inclusion
- Review concomitant medications that the subject has taken within 30 days prior to screening.
- Assess and record pre-dosing signs / symptoms
- Determine study eligibility
- Electrocardiogram
- Liver biopsy may be performed if subject has historical biopsy c/w NASH and biopsy is > 12 months of screening or subject at increased risk for NASH (increased liver enzymes with > 3 features of metabolic syndrome)

- Urinalysis
- Urine drug screen for amphetamine, cocaine and opiate drug screening
- Complete blood samples for:
 1. Complete blood count with differential
 2. Blood chemistry including: alanine aminotransferase (ALT), aspartate aminotransferase (AST), albumin, alkaline phosphatase, bicarbonate, blood urea nitrogen (BUN), calcium, chloride, creatinine, glucose, lactate dehydrogenase (LDH), magnesium, phosphorus, potassium, sodium, total and direct bilirubin, protein, uric acid, and gamma-glutamyl transferase (GGT).
 3. Fasting glucose and insulin level for HOMA-IR
 4. Glycosylated hemoglobin
 5. Prothrombin time and International normalized ratio (INR)

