10.4.7 Criteria for Discontinuation of Study Treatment

Study medication may be discontinued in the following instances

- Intercurrent illness that would, in the judgment of the investigator, affect assessment of clinical status to a significant degree
- Any concern for drug-induced liver injury as defined by change from baseline liver aminotransferases according to the following criteria:
 - ALT or AST > 10 x ULN
 - ALT or AST > 5 x ULN for more than 2 weeks
 - ALT or AST > 3 x ULN and total bilirubin > 2 x ULN or INR > 1.5
 - ALT or AST > 3 x ULN with the appearance of fatigue, nausea, vomiting, right upper quadrant abdominal pain, fever, rash or eosinophilia (> 5%).
- Unacceptable toxicity, as defined in the toxicity management section of the protocol, or toxicity that, in the judgment of the investigator, compromises the ability to continue study-specific procedures or is considered to not be in the subject's best interest.
- Subject request to discontinue for any reason
- Subject noncompliance
- Pregnancy during the study
- Sponsor discretion

- Discontinuation of the study at the request of TaiwanJ. Pharmaceuticals, any Regulatory Authorities or an IRB/IEC.

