13.4.3.2. Other Safety Endpoints

Change from Baseline for each interval-valued laboratory test, vital signs, and other safety related variables will be summarized regarding each scheduled visit. Shift tables will be presented for laboratory values based on the central laboratory normal ranges.

All abnormalities deemed clinically significant by the investigator will be presented in detail and listed by patient identifier. The patients who have no laboratory results at the Screening or post-Baseline visit will be excluded from the change from Baseline and shift table analyses. Treatment effect will be explored by inspection of observed means or rates for the dose groups within each treatment regimen.

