### **6.11.2 Clinical Laboratory Evaluations**

Summary statistics will be provided for safety laboratory tests at baseline and all scheduled post-baseline visits for chemistry, hematology, and urinalysis assessments by treatment group and in total. The change from baseline to post-baseline visits will also be presented.

The number and frequency of subjects with laboratory abnormalities (worst value post first dose for each subject) will be summarized by treatment group and in total. Shift tables from baseline to worst value post first dose will be presented for ALT and AST (>1xULN to ≤2xULN, >2xULN to ≤3xULN, >3xULN) and CK (>1xULN to ≤5xULN, >5xULN to ≤10xULN, >10xULN).

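### The ALT/AST shift tables end in one open >3xULN cell, so they hide further rises in subjects who start there and show none of the protocol's liver thresholds; bilirubin has no shift table

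*SAP*

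**What the plan says.** **Shift tables in the SAP.** Section 6.11.2 specifies: "Shift tables from baseline to worst value post first dose will be presented for ALT and AST". The categories are >1 to 2x, >2 to 3x and >3xULN. The only other analyte named continues the same sentence: "and CK (>1xULN to ≤5xULN, >5xULN to ≤10xULN, >10xULN"). The section also plans by-visit summaries with change from baseline for chemistry, haematology and urinalysis. It plans counts of laboratory abnormalities at the worst post-dose value, but does not define what counts as abnormal.

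**Shift tables in the protocol.** Section 13.4.3.2 is broader: "Shift tables will be presented for laboratory values based on the central laboratory normal ranges". It does not restrict the analytes.

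**Who may enter.** ALT must exceed 40 U/L in women and 60 U/L in men (Protocol 8.1). The exclusion limit is "AST or ALT > 250 U/L" (Protocol 8.2). Protocol 12.4 states that every patient will have raised liver enzymes at baseline.

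**Where the protocol acts.**
- Multiples of ULN: 10.4.7 and 12.4 list ALT or AST above 10xULN, and above 5xULN for more than two weeks.
- Combined criteria: the same lists include "ALT or AST > 3 x ULN and total bilirubin > 2 x ULN or INR > 1.5", and ALT or AST above 3xULN with symptoms or eosinophilia.
- Multiples of the subject's own baseline: 6.3 and 12.4 act at 3x and 5x.

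**What is measured.** Total and direct bilirubin are in the chemistry panel at screening, Day 1 and every later visit (10.3.2 to 10.4.5). INR appears in the screening panel only. Creatine kinase is in no listed panel; the schedule lists CK-18, a different marker.

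**The concern.** Safety is part of the primary objective, and the subjects have liver disease with enzymes that are already raised. A shift table is the display that links each subject's worst value to where that subject began. If its top category opens at a level some subjects occupy on Day 1, the table reports no shift for them however far they rise. If its categories stop below the protocol's action levels, it cannot show how many subjects in each arm reached those levels. Leaving bilirubin out also removes the second half of the combined criterion. A reader comparing arms could then see an apparently flat table while some subjects had risen considerably.

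**Working it through.** The documents give no figure to reproduce here, so the check compares the table cells with the entry limits and action levels, and then estimates how many subjects are affected.

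**1. Where the top cell begins.** The documents do not give the laboratory ULN. I use 40 U/L, which the SAP uses as its alternative normal limit for remission (5.2), and 50 U/L as an assumed laboratory value.

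| ULN (U/L) | Top cell starts at 3 x ULN | Women, entry range in xULN | Men, entry range in xULN |
|---|---|---|---|
| 40 | 120 | 40/40 = 1.0 to 250/40 = 6.25 | 60/40 = 1.5 to 6.25 |
| 50 | 150 | 40/50 = 0.8 to 250/50 = 5.0 | 60/50 = 1.2 to 5.0 |

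The top cell overlaps the eligible range for any ULN below 250/3 = 83 U/L. The possibility of starting in that cell therefore does not depend on the choice between 40 and 50.

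**2. Can each protocol threshold be read from the planned shift tables?**

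| Protocol threshold | Readable? | Why not |
|---|---|---|
| ALT/AST >5xULN for more than 2 weeks | No | inside the open cell; duration not shown |
| ALT/AST >10xULN | No | inside the open cell |
| >3x or >5x own baseline | No | multiples of baseline are not tabulated |
| >3xULN with bilirubin >2xULN or INR >1.5 | No | only the enzyme part has a cell |
| >3xULN with symptoms or eosinophilia | No | only the enzyme part has a cell |

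Protocol 12.4 grades ALT of 5.1-10.0xULN as Grade 3 and above 10xULN as Grade 4. The table cannot separate these two grades from each other or from 3-5xULN.

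**3. An individual example.** At ULN 40, ALT rises from 130 to 420 U/L. That is 130/40 = 3.25xULN to 420/40 = 10.5xULN, and 420/130 = 3.2x baseline. Both values fall in the >3xULN cell, so the subject is tabulated as unchanged.

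**4. Share starting above 3xULN.** Assume log-normal ALT with mean m and SD s before truncation, cut to (L, 250], where L is 40 for women and 60 for men. The SD of 40 is the documents' planning value for baseline ALT (SAP 6.1). The mean of 85-110 and the upper SD of 45 are my assumptions, because the documents give no mean.

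- sigma² = ln(1 + (s/m)²) and mu = ln(m) - sigma²/2
- share = [S(3 x ULN) - S(250)] / [S(L) - S(250)], where S is the upper-tail probability

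Example for women with m = 85, s = 40 and ULN 40: sigma = 0.447 and mu = 4.343. Then S(120) = 0.160, S(250) = 0.004 and S(40) = 0.928, so the share is (0.160 - 0.004)/(0.928 - 0.004) = 0.169.

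| m, s | ULN 40: women / men | ULN 50: women / men |
|---|---|---|
| 85, 40 | 17% / 22% | 7% / 9% |
| 85, 45 | 19% / 25% | 8% / 11% |
| 110, 40 | 33% / 35% | 14% / 15% |
| 110, 45 | 33% / 36% | 15% / 17% |

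The range is 17-36% at ULN 40, or about 10 to 22 of 60 subjects. At ULN 50 it is 7-17%, or about 4 to 10 of 60.

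**The case against.** **Other outputs would show a large rise.** This is the strongest reply.
- Change from baseline is summarised at each visit for all chemistry, bilirubin included, with minimum and maximum (SAP 6.2, 6.11.2).
- Clinically significant laboratory results count as adverse events and are tabulated by maximum severity. Events leading to discontinuation are listed (SAP 6.11.1).
- Protocol 13.4.3.2 lists clinically significant abnormalities by patient.
- An unblinded independent board compares safety with placebo (Protocol 13.6).

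With 20 subjects per arm, outliers can be found in listings. This stands in part. However, a visit maximum does not say how many subjects crossed a threshold or where they began. The abnormality counts have no stated criteria, and the adverse event route depends on the investigator's judgement of significance. The table shells are a separate document (SAP 7) and might add detail, but the SAP text fixes the categories.

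**A reader might infer that most subjects start in the top cell.** That follows if the 20 and 30 U/L limits are taken as the ULN. The documents do not support it: those limits define the ALT remission endpoints, while Protocol 13.4.3.2 bases shift tables on central laboratory ranges. A ULN of 20 would also put the 10xULN withdrawal level for women at 200 U/L, below the 250 U/L entry limit. The synopsis describes baseline ALT as below 5xULN. Set beside 250 U/L, that would suggest a ULN near 250/5 = 50, though this too is only an inference.

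**A reader might infer that CK was put in place of bilirubin.** Nothing says so, and bilirubin remains in the chemistry summaries. The SAP does not expand CK in 6.11.2; its only expansion of those letters is cytokeratin, in 5.3.

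**Conclusion.** The point holds for the shift tables. They have a ceiling inside the eligible ALT range, no protocol liver threshold can be read from them, and bilirubin is left out although it is collected at every visit and the protocol promises shift tables without naming particular analytes. The number of subjects affected is uncertain: 17-36% at ULN 40 and 7-17% at ULN 50, resting on an assumed distribution and an unstated laboratory ULN. Only the existence of the ceiling is free of those assumptions.

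It would go too far to say that the trial cannot detect liver injury. A move from 3xULN or below into the top cell does show, though not its extent, and the other safety outputs give partial cover. No efficacy estimate or test is affected. This is a worthwhile, inexpensive improvement to how a primary safety question is displayed.

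**What to change.** In SAP 6.11.2 and the table shells, using the central laboratory ULN and the cut points the protocol already contains:

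1. Split the top ALT and AST category into >3 to 5x, >5 to 10x and >10xULN.
2. Tabulate each subject's worst post-dose value as a multiple of baseline, with counts above 3x and above 5x.
3. Add a total bilirubin shift table. Add a count of subjects with ALT or AST >3xULN and bilirubin >2xULN, including INR >1.5 where INR was measured. INR is scheduled only at screening, so the table should state how many subjects had an on-treatment value.
4. State which analyte CK means. If it is creatine kinase and is not collected, drop the table.
5. Define the criteria for the laboratory abnormality counts, and explain any remaining restriction relative to Protocol 13.4.3.2.

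The cost is a short SAP edit and a few extra shells, which are due to be finalised before database lock. ALT, AST and bilirubin are already collected. The downside is sparse cells with 20 subjects per arm, so these tables should be read as counts. No clinical threshold is changed or endorsed.

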### **6.11.3 Vital Signs and ECG**

Height, weight, waist circumference, and vital signs will be summarized at baseline and each scheduled post-baseline visit. The change from baseline will also be presented.

The overall ECG interpretation will be summarized by scheduled visit with counts and percentages by treatment group and in total.

### **6.11.4 Other Safety Parameters**

All other safety parameters such as lifestyle, hospital anxiety and depression scale, Columbia-Suicide Severity Rating Scale, physical examination, and pregnancy tests will be listed.

## **7 GENERAL INFORMATION**

The mock-ups for SAS-generated tables/figures/listings will be prepared in a separate document and finalized before database lock for the study.

### **7.1 Statistical Software**

The creation of analysis datasets and all statistical analyses will be done using SAS® version 9.3. The PK parameters will be determined using Phoenix™ WinNonlin® version 6.3 or higher. The Medpace standard operating procedures will be followed for the validation of all SAS programs and outputs.
